### 7.1.4 Serious Adverse Event Reporting

If the site personnel identifies a potential SAE the Investigator will be notified immediately. If the study investigator determines that the adverse event meets the criteria for an SAE, the Investigator will report the event as follows: document the SAE in the adverse event log. t The study investigator will also notify the KPSC Institutional Review Board (IRB) of unanticipated SAEs within 10 business days per the KPSC IRB SOP 502, Principal Investigator Reportable Event and Incident Requirements.

8 STUDY SCHEDULE: CLINICAL/ LABORATORY EVALUATIONS

# 8.1 Study Procedure

8.1.1 Informed Consent

Subjects will typically have the time between their clinic initial/consultation visit and their procedure appointment (typically at least 1 week) to consider whether to consent. If the study is not discussed at their prior visit or via telephone script prior to procedure appointment, subjects will be given up to 60 min to consider and ask the Investigator questions. Participants will be consented by the Principal Investigator or any of the physician co-investigators who will be performing the Botox® procedure. The participant will be provided a copy of the signed informed consent.

8.1.2 Eligibility Review

Eligibility will be assessed by review of inclusion and exclusion criteria posted in all recruitment locations by co-investigators. After consent and enrollment the participants will be screened and randomized via permuted blocks in a 1:1 fashion to either the study group (1 injection) or the control group/standard of care (10 injections). The pre-assigned randomization by permuted block design will be determined at the time of the procedure by opening of a sealed, opaque envelope containing the group allocation.

**Pre-Procedure Requirements** 

Prior to the procedure each subject will have the following (at either prior/consultation visit or procedure visit see study calendar below):

[] sign consent form
(prior to any non-standard of care procedures)
[] Post-void residual
[] Urinalysis (formal UA OR poct udip)
[] OAB-Q LF Questionnaire completion

[figure not shown]

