### 4.4 Concomitant Medications/ Treatments

Current treatment with either: SNM, PTNS, or OAB medications – need wash out as below:

- 1 SNM turn device off for at least 2 weeks prior to procedure, off during 3-month follow up window
- 2 PTNS no treatments within 2 weeks of start, none during 3-month post-procedure follow up window
- 3 OAB meds 2 week wash out period prior to injection, none during 3-month post-procedure follow up window

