### Exclusion Criteria

- 1 Have a diagnosis of neurogenic bladder
- 2 Received intravesical Botox® injections within prior 6 months
- 3 Current treatment with either: SNM, PTNS, or OAB medications need wash out as below
- 4 SNM turn device off for at least 2 weeks prior to procedure, off during 3-month follow up window
- 5 PTNS no treatments within 2 weeks of start, none during 3-month post-procedure follow up window
- 6 OAB meds 2 week wash out period prior to injection, none during 3-month post-procedure follow up window
- 7 Currently pregnant or trying to get pregnant
- 8 Contraindications to Botox® hypersensitivity to Botox®, inability to self-catheterize/refusal to have indwelling catheter
- 9 Have a UTI (can enroll after treatment)
- 10 Have urinary retention (PVR>150cc on two occasions)
- 11 Do not speak English or Spanish

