1. Procedure visit for intradetrusor Botox® injection, collection of pre-procedure OAB-q, VAS pain scale after procedure

2. 3-week follow up visit, including collection of post-void residual via urethral catheterization or bladder scan (ultrasound) and post-procedure OAB-q

3. 3-month follow up visit, either in person or via telephone with collection of OAB-g and symptoms improvement questionnaire (PGI-I)

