#### 8.4 Schedule of Assessments

Procedures	]			
	Consultation clinic visit (prior to study enrollment)	Procedure Visit	3 wk Follow-Up	3 month Follow-Up
Estimated visit time	60min	60 min	60 min	60 min
Recruit	Х			
Urinalysis	Х			
PVR	Х		Х	
Sign Consent	X	OR X		
Questionnaire (OAB-q LF)	Х	OR X	X	
VAS-Pain Score		X (after procedure)		

Protocol Number: Intradetrusor Botulinum Toxin A: Are less injections better? V2 09 Mar 2022 Investigator Initiated Clinical Trial Protocol

Questionnaire (OAB-q LF, PGI-I)		Х
Telephone Call (if		Х
unable to present for		
in-person visit)		

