### 9.1 Primary Endpoints

The primary outcome variable will be the OAB-q symptoms severity subscale score (urinary symptom questionnaire) as a marker of efficacy.

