### 9.2 Secondary Endpoints

The secondary outcome variables will include UTI rate, PVR, urinary retention, interinjection interval, catheter use within 3 months, PGI-I, and VAS pain score.

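### The baseline OAB-q may be completed before washout, which can add a little noise to the change score; tying it to the procedure visit is a minor, nearly free improvement

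*Combined protocol and SAP*

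**What the plan says.** The Pre-Procedure Requirements checklist in Section 8.1.2 includes the OAB-Q LF among items to be done "at either prior/consultation visit or procedure visit see study calendar below". The calendar in Section 8.4 marks the questionnaire under both visits as alternatives, and heads the first column "Consultation clinic visit (prior to study enrollment"). Section 8.2.1 differs: its visit list puts "collection of pre-procedure OAB-q" under the procedure visit and does not mention the consultation.

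Patients on other treatment may enrol after washout. Section 4.4 has "OAB meds 2 week wash out period prior to injection", and the Exclusion Criteria in Section 5 have "SNM turn device off for at least 2 weeks prior to procedure, off during 3-month follow up window"; PTNS has a parallel rule. All three treatments stay off through the 3-month window, so the 3-week score is off therapy by design. No passage says that the baseline form must follow the washout.

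Section 12.1 frames the hypothesis as the change in symptom severity from pre-procedure to 3 weeks. Section 12.3 first applies a t-test to the OAB-Q score, then fits models that adjust for baseline severity. Section 9.1 says "The primary outcome variable will be the OAB-q symptoms severity subscale score", without saying whether that means the 3-week score or the change. Allocation is "determined at the time of the procedure by opening of a sealed, opaque envelope" (Section 8.1.2).

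**The concern.** A patient is affected only if three things hold together: she is on OAB medication, SNM or PTNS at the consultation, she has not yet stopped, and she completes the form there. Her baseline is then on therapy and at least 2 weeks old at injection, because she must still wash out. Her 3-week score is off that therapy. Her change score mixes the effect of the injection with the effect of stopping the earlier treatment.

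Other patients have a baseline and a 3-week score taken in the same treatment state. Pooling the two kinds of patient widens the spread of the change score and weakens baseline as a covariate. If the stopped therapy was working, the average improvement reported within each arm would also be too small. That is descriptive only. Within-arm improvement is not a named endpoint in Section 9.1, nor in the Section 9.2 list that begins "The secondary outcome variables will include UTI rate, PVR, urinary retention". It would still be read with interest, because the trial has no placebo arm.

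**Working it through.** **Inputs from the documents.** SD 20, minimal important difference 10, 51 per arm, 80% power, 5% level (Section 12.2); the contrast is change to 3 weeks (Section 12.1).

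**Assumptions.**
- The 10 points serve as the non-inferiority margin, and the true difference is 0.
- The test is one-sided at 5%. The documents do not state the side.
- The SD of change is 20. This follows from a score SD of 20 at both times and a correlation r of 0.5: sqrt(2 × 400 × (1 − 0.5)) = 20.
- A share p of all patients has an on-therapy baseline, shifted by d points. Neither p nor d is in the documents.

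**Step 1: reproduce the plan's figure.** With n per arm, the noncentrality is 10 / (20 × sqrt(2/n)). The noncentral t gives 79.9% power at n = 50 and 80.6% at n = 51. The stated 51 is reproduced, so one-sided 5% is the reading consistent with the plan.

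**Step 2: change score.** A shift of d in a random share p adds variance p(1 − p)d², so SD = sqrt(400 + p(1 − p)d²). Within-arm improvement moves by p × d.

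| p | d | Added variance | SD | Power at 51 per arm | p × d |
|---|---|---|---|---|---|
| 0 | 0 | 0 | 20.00 | 80.6% | 0 |
| 10% | 5 | 2.25 | 20.06 | 80.4% | 0.5 |
| 25% | 5 | 4.69 | 20.12 | 80.2% | 1.25 |
| 25% | 10 | 18.75 | 20.46 | 79.0% | 2.5 |
| 50% | 10 | 25 | 20.62 | 78.5% | 5 |
| 50% | 20 | 100 | 22.36 | 72.5% | 10 |

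At 25% and 10 points, 52 per arm falls just short of 80% and 53 reaches it.

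**Step 3: baseline-adjusted model.** With r = 0.5 the covariance is 0.5 × 400 = 200. The residual SD is 20 × sqrt(1 − 200² / (400 × (400 + p(1 − p)d²))). It is 17.32 with no shift, 17.34 at 10% and 5 points, and 17.45 at 25% and 10 points. The power losses in the two shifted cases are 0.05 and 0.40 points.

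**Step 4: other correlations.** Keep the score SD at 20 at both times and vary r from 0.3 to 0.7. The change-score loss stays at about 0.2 points for 10% and 5 points, and between 1.2 and 1.6 points for 25% and 10 points. The adjusted loss at 25% and 10 points is 0.14, 0.40 and 0.55 points at r = 0.3, 0.5 and 0.7.

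**Step 5: bias.** A consultation form is completed before the envelope is opened, so the on-therapy share is equal between arms in expectation. Simulation (40,000 trials per setting, p = 50%, d = 10 or 20) gave a mean between-arm difference of about 0.01 when the truth was 0 and about 10.0 when it was 10. Type I error at the margin was 0.051 and 0.048.

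**The case against.** **The effect is close to nil.** There is no bias, the loss is under 2 points in the illustrative range, and it is smaller after adjustment. An unadjusted comparison of 3-week scores, which Sections 9.1 and 12.3 also permit as a reading, is untouched. If the literature SD of 20 already includes baselines of mixed timing, the loss against planned power may be nothing. All of this stands, and it limits the point to a minor one.

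**The plan may already handle it.** Section 8.2.1 puts the form at the procedure visit, and Section 12.3 allows adjustment for other baseline measures. A covariate marking the affected patients would absorb a constant shift. But prior therapy is not named as a covariate, and Section 8.2.1 sits beside two places that allow the consultation.

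**Few patients may qualify.** Section 8.1.1 puts the procedure typically at least 1 week after the consultation. Anyone injected within 2 weeks of consultation must already have stopped therapy by then, and so is unaffected. This stands too; the remaining share is unknown.

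**Stronger readings.** A reader might infer that the arms are compared unfairly; the order of baseline and allocation rules that out. A reader might take 72.5% as the expected power; it needs half of all patients affected by 20 points, and the documents support neither figure. For the same reason the documents do not prove the effect small. Nor do they show that improvement is understated: that needs the stopped therapy to have been working. Finally, a reader might infer that noise must make non-inferiority harder to show. That holds only for a test against a margin. Section 12.3 names only a t-test between arms, and if a non-significant result were read as similarity, noise would push the other way.

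**Conclusion.** The point holds as a minor improvement. The documents allow an on-therapy baseline for some washout patients, and Section 8.2.1 does not agree with the checklist and calendar. The consequence is extra noise in the change score and a slightly weaker baseline covariate, without bias between arms.

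Under the illustrative range, the change-score comparison loses 0.2 to 1.6 points of power, and the adjusted model at most 0.4 points at r = 0.5. These figures rest on a margin of 10, one-sided 5%, an SD of change of 20, and an assumed share and shift. The planned 51 per arm clears 80% by only 0.6 points, so the upper case falls just below target. The reason to act is that the change is cheap and that a post-washout baseline cannot be recovered once the patient has been injected.

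**What to change.** Reconcile the Section 8.1.2 checklist and the Section 8.4 calendar with Section 8.2.1. Suggested wording: 'The analysis-baseline OAB-q is completed, or repeated, at the procedure visit before the allocation envelope is opened.' Apply it at least to every patient who needed washout. Applying it to all patients is simpler and keeps baseline timing from differing by prior therapy. State in Sections 12.1 and 12.3 that this score is the baseline.

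Two checks need appendices that are not among the documents. Compare the recall period of the OAB-Q LF (Appendix C) with the washout period: if recall is longer than washout, a procedure-visit form would still cover some on-therapy days and the repair would be partial. Confirm that the case report form (Appendix A) records the date of the form and therapy status at completion.

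The cost is wording in four or five places. Patients who completed the form at consultation repeat it once, at a visit where it is already allowed. There is no new visit, the sample size is unchanged, and no washout or other clinical rule changes.

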# 8.1.3 Study Procedure

Botox Injection Procedure

### Arm 1: 1 injection

Subjects will be blinded to the allocation group by turning the cystoscope screen away from patient. Cystoscopic injection will be standardized using an injection cystoscope and 100-200 mL of intravesical fluid. Subjects undergoing the procedure in clinic will receive a lidocaine instillation prior to the procedure along with a urethral lidocaine jelly. The physician will inject 10 mL of (100u/10mL) Botulinum Toxin A in one midline, supra-trigonal posterior bladder wall site at a depth of 3mm, as diagramed below. The bladder trigone and ureteral orifices will not be injected. Each subject will undergo a single injection procedure as part of this trial. Each subject will void prior to leaving clinic.

Arm 2: 10 Injections

Subjects will be blinded to the allocation group by turning the cystoscope screen away from patient. Cystoscopic injection will be standardized using an injection cystoscope and 100-200 mL of intravesical fluid. Subjects undergoing the procedure in clinic will receive lidocaine instillation prior to the procedure along with a urethral lidocaine jelly. The physician will inject 10 mL of (100u/10mL) Botulinum Toxin A in ten 1mL aliquots at ten supra-trigonal posterior bladder wall sites at a depth of 3mm, as diagramed below. The bladder trigone and ureteral orifices will not be injected. Each subject will undergo a single injection procedure as part of this trial. Each subject will void prior to leaving clinic.

[figure not shown]

Figure 2: Arm 2: 10 injection locations

Post-Procedure Requirements [] Confirm ability to void after procedure

[] Subject completes visual analogue scale of pain

[] Procedure note using study dotphrase: .procbotoxstudy

[] RX prophylactic antibiotic

Macrobid 100 mg BID x 3 day

OR 2nd line if allergies

- Bactrim DS BID x 3 day

3 week follow up visit

[] PVR [] OAB-Q LF 3 month follow up visit

> [] OAB-Q LF [] PGI-I

- 8.2 Clinical Evaluations
  - 8.2.1 Clinical Evaluation

Subjects will be screened at their initial consultation visit for inclusion in the study. If the screening exams, tests and/or procedures allow and the subject desires to enroll, then the subject will have the following procedures and tests done. This study includes 3 visits which will take

about 60 minutes each. These will include a procedure visit, a 3-week follow up visit, and a 3 month follow up.

1. Procedure visit for intradetrusor Botox® injection, collection of pre-procedure OAB-q, VAS pain scale after procedure

2. 3-week follow up visit, including collection of post-void residual via urethral catheterization or bladder scan (ultrasound) and post-procedure OAB-q

3. 3-month follow up visit, either in person or via telephone with collection of OAB-g and symptoms improvement questionnaire (PGI-I)

#### 8.2.2 Adverse Event Assessment

Participants will be assessed for adverse events from the time of their injection procedure through at least 3 months post procedure. There will be specific evaluation for urinary retention (PVR collected at 3 week follow up visit) and UTI (UA pre-procedure and UCx post-procedure if symptomatic). See Section 7.1 regarding adverse event reporting.

#### 8.3 Laboratory Evaluations

8.3.1 Insert Laboratory Evaluation

> A standard of care lab urinalysis or clinic point of care urine dip evaluation will be collected prior to the Botox® injection procedure. There will not be any other standard required labs. If participants are exhibiting UTI symptoms, a standard of care work up with urine culture will be completed.

#### 8.4 Schedule of Assessments

Procedures	]			
	Consultation clinic visit (prior to study enrollment)	Procedure Visit	3 wk Follow-Up	3 month Follow-Up
Estimated visit time	60min	60 min	60 min	60 min
Recruit	Х			
Urinalysis	Х			
PVR	Х		Х	
Sign Consent	X	OR X		
Questionnaire (OAB-q LF)	Х	OR X	X	
VAS-Pain Score		X (after procedure)		

Protocol Number: Intradetrusor Botulinum Toxin A: Are less injections better? V2 09 Mar 2022 Investigator Initiated Clinical Trial Protocol

Questionnaire (OAB-q LF, PGI-I)		Х
Telephone Call (if		Х
unable to present for		
in-person visit)		

# 9 CRITERIA FOR EVALUATION AND ENDPOINT DEFINITIONS

The outcome status (in terms of toxicity, response, reason off study, progression, and survival) of all eligible patients will be reported. All eligible patients who begin treatment will be included in the analysis of efficacy, safety, and tolerability of the Botox® procedure.

### 9.1 Primary Endpoints

The primary outcome variable will be the OAB-q symptoms severity subscale score (urinary symptom questionnaire) as a marker of efficacy.

### 9.2 Secondary Endpoints

The secondary outcome variables will include UTI rate, PVR, urinary retention, interinjection interval, catheter use within 3 months, PGI-I, and VAS pain score.

### 10 DATA HANDLING AND RECORD KEEPING

10.1 Source Documentation

Documentation that will be considered as source will be the electronic medical records and questionnaires (OAB-Q, PGI-I, and VAS-pain).

### 10.2 Case Report Forms

10.3 CRF attached as appendix. The electronic medical record and questionnaires (OAB-Q, PGI-I, and VAS-pain) will be considered data sources. Study data will be captured using REDCap for data management purposes. Record Retention

Data will be stored securely in REDCap and retained through presentation and publication of study results. At site for 1 year after the IRB has closed out the study. Following that all study related documents will be archived for 15 years at Iron Mountain Retention facility ([name]).

10.4 Data Management

Data will be stored securely in KPSC REDCap. This data will be encrypted and password protected on the KPSCnetwork via REDCap. Only delegated study personnel will have access to the database.

# 11 STUDY OVERSIGHT

# 11.1 Data Safety Monitoring Board

An independent Data Safety Monitoring Board (DSMB) has been chartered and will meet as specified in the DSMB charter agreement to assist with safety oversight. The DSMB will report back to the PI. See Appendix D, DSMB Charter for details.

### 11.2 Study Site Monitoring

Internal monitoring of sites will be conducted quarterly by the PI and site lead investigators, [name], [name], [name], respectively. The monitoring will be done remotely through scheduled teleconferences with the lead investigator and/or designee. On-site visits will also be conducted quarterly. See satellite site management plan, appendix E for details.

# 12 STATISTICAL CONSIDERATIONS

# 12.1 Study Hypothesis

We hypothesize that one intradetrusor Botox® injection site has similar efficacy to ten injections sites based on OAB-Q symptoms severity score change from pre-procedure to 3-week post-procedure with a minimal clinical important difference of 10.

### 12.2 Sample Size Considerations

The target sample size was determined by using the typical standard deviation of the OAB-q symptom severity score (20 points per literature review) and the known minimally important clinical difference of 10 points of the OAB-q severity subscale, our primary outcome. Using this data, we calculated the sample size of N=102 maximum total (expect to enroll ~40 at KP, ~60 at UCI, ~20 PSJH), 51 subjects in each arm for an 80% power with 5% significance level. Based on review of prior clinical data at UCI and KP, we expect to complete enrollment within 1 – 1.5 years. With an estimated 15% lost to follow up rate, we calculated need to enroll 116 subjects.

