# 3 STUDY DESIGN

We plan for a prospective, single-blinded, non-inferiority randomized controlled trial. We will evaluate the efficacy, safety, and tolerability of one intradetrusor Botox® injection (study) versus ten injections (control/standard of care). The patient will be blinded. There will be 1:1 randomization. The physician doing the procedure will not be blinded.

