### 12.3 Final Analysis Plan

We will describe the study population, including patient age, race/ethnicity, baseline severity scores (OAB-Q), BMI, medical history (prior surgery, menopausal status, prior Botox, etc.), overall, by arm, and stratified by study site (KPSC, UCI, PSJH). We will summarize continuous measures using means and standard deviations and categorical measures using percentages. We will compare study arms using the t-test or Fisher's exact test, as appropriate.

We will examine the outcome measures (OAB-Q and any secondary measures) to determine whether they are approximately normally distributed. If not, we will apply a

transformation prior to analysis to make the analytic variable approximately normal. If no transformation successfully achieves approximate normality, we will apply non-parametric tests for analysis, including Wilcoxon's rank-sum test instead of the t-test and quantile regression instead of linear regression.

We will analyze the main study outcome (OAB-Q score) initially using a t-test to compare the two study arms, overall and stratified by study site. We will further analyze the outcome using generalized estimating equations to account for correlation within study sites. These models will adjust for any potential differences in age, race/ethnicity, baseline severity scores, or any other baseline measures, and will account for any potential differences between study sites.

Secondary outcomes will be analyzed in the same manner as the primary outcome.

Primary analyses will be performed using intention-to-treat to determine study arm. If multiple individuals are not treated according to the randomization plan, we will perform a sensitivity analysis using as-treated, per-protocol study arms.

For any individuals who are lost to follow-up, we will first compare those individuals who are lost to those who complete follow-up in terms of demographics, baseline characteristics and any outcome assessments prior to the time that they are lost to follow-up. For primary analysis of OAB-Q scores, we will analyze complete data including only those who have completed the follow-up questionnaires within the prescribed timeframes. If more than 10% are lost to follow-up, we will additionally perform multiple imputation in an attempt to capture data of those lost to follow-up.

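### The sample size uses the SD of the score, the hypothesis concerns change, and 12.3 names neither the variable tested nor the deciding analysis; one fixed baseline-adjusted model would settle this without new data.

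*Combined protocol and SAP*

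**What the plan says.** Section 3 describes a "prospective, single-blinded, non-inferiority randomized controlled trial". Section 12.2 gives the basis of the sample size: "The target sample size was determined by using the typical standard deviation of the OAB-q symptom severity score (20 points per literature review"). It also uses the "known minimally important clinical difference of 10 points of the OAB-q severity subscale, our primary outcome". The result is "51 subjects in each arm for an 80% power with 5% significance level". Whether the 5% is one-sided or two-sided is not stated.

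Section 12.1 frames the hypothesis on "OAB-Q symptoms severity score change from pre-procedure to 3-week post-procedure". The Protocol Summary, 2.1 and 9.1 name the primary outcome only as the symptom severity subscale score, with no mention of change and no time point.

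The analysis in 12.3 comes in two steps. The first is: "We will analyze the main study outcome (OAB-Q score) initially using a t-test to compare the two study arms". The second is a set of GEE models, intended to handle correlation within site, which will "adjust for any potential differences in age, race/ethnicity, baseline severity scores, or any other baseline measures". Section 12.3 names three sites. Neither step is called the primary non-inferiority analysis, and no section gives an SD of change or a correlation between baseline and 3-week scores.

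**The concern.** The SD of a score at one visit and the SD of a change between two visits are different quantities. They coincide only at a particular correlation. A plan that takes its SD from the score and its hypothesis from the change has an unstated correlation inside its power claim, unless the test is in fact done on the 3-week score.

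The second issue does not depend on that correlation. The t-test and the GEE models will give different estimates of the treatment difference, and the closing words of the covariate list allow further versions of the GEE estimate. Nothing says which of these is to be compared with the 10-point margin. In a non-inferiority trial, where the conclusion rests on one confidence bound, that choice should be made before the data are seen.

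**Working it through.** **Inputs.** From 12.2: SD 20, margin 10, 51 per arm, 80% power, 5% significance. From section 3: non-inferiority, 1:1 allocation. Assumed, because the documents do not say: true difference 0, SD 20 at both visits, r from 0.2 to 0.7.

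**Reproducing the plan's figure.** Power is from the noncentral t with noncentrality 10 / (SD × √(2/n)). With SD 20 and n = 51 this is 10 / (20 × √(2/51)) = 2.52 on 100 degrees of freedom.

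- One-sided 5%: power 80.6%, and 51 is the smallest n per arm that reaches 80%. This matches the plan.
- One-sided 2.5% (two-sided 5%): power 70.6%, and 64 per arm would be needed. This does not match.

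One-sided 5% is therefore the setting used below.

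**Three possible analyses.** With SD 20 at both visits:

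- t-test on the 3-week score: SD = 20 at every r.
- t-test on change: SD = 20 × √(2(1 − r)). This equals 20 only at r = 0.5. It is larger below that and smaller above.
- Linear model of the 3-week score with baseline as covariate: residual SD = 20 × √(1 − r²).

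Example at r = 0.3: change SD = 20 × √1.4 = 23.7; residual SD = 20 × √0.91 = 19.1.

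| r | SD of change | Power, t-test on change | Power, t-test on 3-week score | Residual SD, adjusted | Power, adjusted |
|---|---|---|---|---|---|
| 0.2 | 25.3 | 63% | 80.6% | 19.6 | 82% |
| 0.3 | 23.7 | 68% | 80.6% | 19.1 | 84% |
| 0.4 | 21.9 | 74% | 80.6% | 18.3 | 86% |
| 0.5 | 20.0 | 81% | 80.6% | 17.3 | 89% |
| 0.6 | 17.9 | 88% | 80.6% | 16.0 | 93% |
| 0.7 | 15.5 | 94% | 80.6% | 14.3 | 97% |

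The adjusted column charges one degree of freedom for baseline. Charging two more for three sites leaves every rounded entry unchanged.

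**Why adjustment does at least as well as either t-test.** Since 1 − r² = (1 − r)(1 + r) and 1 + r ≤ 2, the residual SD cannot exceed the SD of change. Since 1 − r² ≤ 1, it cannot exceed 20. The only price is the degrees of freedom.

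**Why adjustment settles which variable is analysed.** If Y is the 3-week score and B the baseline, replacing Y by Y − B in a model that contains B lowers the coefficient of B by 1. The arm coefficient and its standard error do not change.

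**Sensitivity to the assumptions.**

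- *Unequal SDs.* If the baseline SD is 20 and the 3-week SD is k × 20, the SD of change equals 20 at r = k/2: 0.4 for k = 0.8, and 0.6 for k = 1.2. With a 3-week SD of 24 (k = 1.2), adjusted power is 67% at r = 0 and 71% at r = 0.3.
- *Completers.* 116 × 0.85 = 98.6, or about 49 per arm. Adjusted power is then 79.2% at r = 0 and reaches 80% from r of about 0.16.
- *Sidedness.* At one-sided 2.5% with 51 per arm, adjusted power is 70.6% at r = 0 and reaches 80% from r of about 0.46.

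**The case against.** The strongest reply is that the power calculation may be right as it stands. Only the hypothesis in 12.1 mentions change. The endpoint sections and the t-test sentence in 12.3 refer to the score. If the t-test is on the 3-week score, SD 20 is the matching input and power is 80.6% at every r. This stands. A reader might infer from 12.1 and 12.2 that the stated 80% power is lost, but the documents do not support that. The loss needs both a test on change and a correlation below 0.5, and neither is established. Above 0.5 a test on change has more power than planned. The source of the SD is a literature review whose visit or visits are not given, so SD 20 at both visits is itself an assumption.

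It can also be said that 12.3 already adjusts for baseline severity and site. It does, and much of the covariate sentence can be read as a named list. But the list ends open, the adjusted models come second, and they are not designated as deciding. GEE is also a weak basis for handling site here, because its robust variance is unreliable with three clusters.

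Finally, a reader might infer that baseline adjustment guarantees 80% power whatever the correlation. It does not. The sensitivity figures show it falling short with a larger 3-week SD, with fewer completers at low r, or at one-sided 2.5%.

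**Conclusion.** The point holds as a gap in specification with a conditional effect on power. The SD is described as that of the score, the hypothesis is on change, the variable in the t-test is not stated, and no analysis is named as deciding non-inferiority. Depending on the reading, power at the planned size is either 80.6% throughout or anywhere from 63% to 94% for r between 0.2 and 0.7. The direction of any error is unknown, because r is not given. These figures assume SD 20 at both visits, 51 completers per arm, a true difference of 0 and one-sided 5%.

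On those same assumptions a baseline-adjusted primary model has 82% to 97% power over that range. It is at least as powerful as either t-test, apart from a negligible loss of degrees of freedom. The lack of a single deciding analysis is a defect at any r. The trial is not invalidated, but the change should be made before the data are analysed.

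**What to change.** In 12.3, name one primary analysis: a linear model of the 3-week OAB-q symptom severity score on arm, baseline score and site, with site as fixed effects. Compare the confidence bound for the adjusted arm difference with the 10-point margin. Fix the covariates in advance and add none because of observed imbalance. Keep the unadjusted t-test and the GEE models as supportive analyses.

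In 9.1 and 12.1, give the primary outcome the same variable and time point as the model.

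In 12.2, state whether the 5% is one-sided or two-sided; the bound used in 12.3 must follow that choice. State which visit or quantity the SD of 20 describes and what correlation, if any, was assumed. Say that SD 20 is a conservative planning value for the adjusted model only if the 3-week SD is no more than about 20 and about 51 per arm complete.

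The cost is protocol and SAP wording. The pre-procedure questionnaire is already required for registration (section 13), the 3-week questionnaire is already scheduled (8.4), and site is already an analysis variable (12.3). No patients, visits or measurements are added by the change of model.
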